6 GENERAL ANALYSIS DEFINITIONS

6.1 TREATMENTS

For all cohorts: Patients will be analysed according to the cohort initially assigned. All planned analysis will be presented by this cohort, unless specified otherwise. Handling of patients where cohort assignment has not been followed will be handled on a case-by-case basis, to be agreed at report planning meetings or DBL meeting (but prior to database lock).

For Cohort A, B, C and D, different dose levels of Xentuzumab and Abemaciclib will arise. The data will be presented for all cohorts separately. To justify the MTD determination, DLTs occurring during the MTD evaluation period will be presented separately from those occurring during the complete on-treatment period.

For the on-treatment period and the MTD evaluation period, the initial trial medication assigned at the beginning of the first treatment cycle will be used as label of the analysing treatment.

For safety summaries data recorded during the Residual Effect Period (REP) will be considered as on-treatment. For this trial, the length of the REP is 42 days.

The actual study periods and treatment codes are defined in a document entitled “4-12-01-sdtm-trial-arms-trial-elements-trial-visits”, which can be found in Data Management and Statistics (DMS) folder, Section 4, within BIRDS.

Patients in cohorts E and F are on continuous daily abemaciclib for a 9-days run-in period. For these patients, the on-treatment period is considered to the start of run-in period.

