5.6 OTHER ASSESSMENTS

The following patient demographic, baseline characteristics and medical history will be collected on the eCRF:

1. General demography including sex, birth date and race as allowed by local law, information on smoking and alcohol history. Collection of race and/or ethnic information is necessary in this study because this is a multi-national trial and race and/or ethnicity are known to be associated with biology and outcome of breast cancer and NSCLC. Foreign regulatory agencies may request data or analysis based on race/ethnic information.
2. Medical history/current medical conditions (including history of menopause, prior and concomitant medications and concomitant diagnosis)

3. History and current disease status including date of first histological diagnosis (month and year may be sufficient), type of tumour histology, tumour grade, other diagnosis information such as mutations or receptors overexpression, known tumour genetic alterations, TNM staging, number and locations of metastatic sites (bone, liver, lung, peritoneum, brain, other) at the study entry
4. Previous anticancer treatments: previous surgery, hormonotherapy, chemo-, targeted, or radiation therapy will be reported including setting (neoadjuvant vs. adjuvant vs. therapeutic), start and end dates (month and year may be sufficient), the therapy protocol with the number of courses (chemotherapy), total radiation dose and radiation field (radiotherapy), the best response obtained (complete response, partial response, stable disease/non-CR/non-PD, progressive disease, unknown) and reason for treatment discontinuation

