7. STATISTICAL METHODS AND DETERMINATION OF SAMPLE SIZE

7.1 STATISTICAL DESIGN - MODEL

This trial will be performed as an open-label study. The primary objective of the dose finding cohorts of this trial is to determine the MTD and the RP2D of:

- * Cohort A: xentuzumab in combination with abemaciclib (without endocrine background therapy)
- * Cohort B: xentuzumab in combination with abemaciclib on a background therapy of letrozole
- * Cohort C: xentuzumab in combination with abemaciclib on a background therapy of anastrozole
- * Cohort D (dose finding): xentuzumab in combination with abemaciclib on a background therapy of fulvestrant

To determine the MTD, patients are entered sequentially into escalating or de-escalating dose-level cohorts. For each treatment combination, the dose finding will be guided by a Bayesian 5-parameter logistic regression model with overdose control ([R15-4233, Chapter 6](#)).

This logistic regression model is defined as follows. Let $\pi_{1,d1}$ be the probability of having a DLT when giving dose d_1 of xentuzumab as monotherapy, and $\pi_{2,d2}$ the probability of having a DLT when giving dose d_2 of the combination partner abemaciclib as monotherapy, respectively. A logistic regression is used to model the dose-toxicity relationship for each of these drugs individually:

Xentuzumab: $\text{logit}(\pi_{1,d1}) = \log(\alpha_1) + \beta_1 \log(d_1/d_1^*)$

Abemaciclib: $\text{logit}(\pi_{2,d2}) = \log(\alpha_2) + \beta_2 \log(d_2/d_2^*)$

Here, the doses $d_1^* = 1000$ mg i.v. once weekly and $d_2^* = 150$ mg every 12 hours represent the reference doses for xentuzumab and abemaciclib, respectively.

Assuming no toxicity interaction between the two compounds, the probability of a DLT when giving the combination dose d_1, d_2 is obtained as

$$\pi_{12,d1,d2}^0 = \pi_{1,d1} + \pi_{2,d2} - \pi_{1,d1}\pi_{2,d2}$$

with corresponding odds

$$\text{odds}(\pi_{12,d1,d2}^0) = \pi_{12,d1,d2}^0 / (1 - \pi_{12,d1,d2}^0).$$

In order to account for a potential positive (higher toxicity than expected under independence) or negative (lower toxicity than expected under independence) interaction between xentuzumab and abemaciclib, a dose-dependent interaction term $-\infty < \eta < \infty$ is introduced in the model by the following definition:

$$\text{odds}(\pi_{12,d1,d2}) = \text{odds}(\pi_{12,d1,d2}^0) \exp(\eta d_1/d_1^* d_2/d_2^*)$$

and $\pi_{12,d1,d2}$ is used in the likelihood

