6.2 IMPORTANT PROTOCOL DEVIATIONS

No per protocol set (PPS) analysis will be performed for this study, hence, no patient will be excluded from the analyses (except those with missing informed consent or not adhering to age limit). However patients with potentially important protocol deviations (IPDs) will be documented. The following list of potentially IPDs in [Table 6.2: 1](#) will be used; note that this is a working list and may not be finalised until the final Blinded Report Planning Meeting (BRPM) or DBL meeting (but prior to database lock for the primary analysis). Potentially important protocol deviations will be handled according to BI standards ([8](#)).

During the study conduct, protocol deviation should be monitored and guidance for improving / teaching the respective sites should be discussed during the study Medical Quality Review Meetings (MQRMs).

A frequency table of the IPDs will be produced. In addition, a frequency table of all COVID-19 related non-important and important PDs will be produced.

Proprietary confidential information © 2021 Boehringer Ingelheim International GmbH or one or more of its affiliated companies

Table 6.2: 1 Important PDs

Category /Code		Description	Requirements	Exclude d from
A [1]		Entrance criteria not met		
	A1	Diagnosis of trial disease questionable	Cohort A and E: Inclusion criteria IN6 is not met. or Cohort B, C, D, F, D1 and D2: Inclusion criteria IN6-8 is not met.	None

Proprietary confidential information © 2021 Boehringer Ingelheim International GmbH or one or more of its affiliated companies

Category /Code	Description	Requirements	Exclude d from
A2	Prohibited baseline condition, diagnosis or treatment	
All Cohorts: Inclusion criteria IN3-5 is not met or Cohort A: Inclusion criteria IN7-8 is not met or Cohort B, C, D, F, D1 and D2: Inclusion criteria IN9-12 is not met or Cohort E: Inclusion criteria IN7-9 not met or Cohort F: Inclusion criteria IN13-14 not met or All cohorts: At least one of exclusion criteria EX1, EX3, EX5-6, EX10, EX12-13, EX15-19, EX21, EX25 is met. or Prohibited medication use (or surgery) before the treatment period of the trial, that is, All cohorts: At least one of exclusion criteria EX4, EX7-9, EX11, EX20, EX22-24 is met
	None
A3	Laboratory result indicating inadequate organ function at screening	
All cohorts: Exclusion criteria EX14 is met or Both screening and baseline (defined in Section 6.7 of this document) laboratory results are missing.
	None

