Proprietary confidential information © 2021 Boehringer Ingelheim International GmbH or one or more of its affiliated companies

Category /Code		Description	Requirements	Exclude d from
B [1]		Legal Criteria		
	B1	Informed consent not available / not done	Written informed consent is not available/done	All
	B2	Informed consent too late	Inclusion criterion IN2 is not met.	None
	B3	Age limit for patient inclusion not adhered to	Inclusion criterion IN1 is not met.	All
C [2]		Trial medication and randomisation		
	C1 [2]	Time window deviation for procedures performed at screening	Assessment at screening not within 28 days prior to first treatment. Create listing, decision at MQRM / RPM.	None
	C2 [2]	Trial medication not given according to protocol	Dose reduction scheme not followed (see CTP Section 4.1.4.2); Administration of trial medication(s) not compliant Indicated by medical review (i.e. where Administration of xentuzumab according to the protocol = 'No' and associated comments, or compliance data from letrozole, anastrozole, fulvestrant or abemaciclib with associated comments) Please note: This excludes the investigational treatment given outside the boundaries specified in the CTP (covered in Category C3).	None

Proprietary confidential information © 2021 Boehringer Ingelheim International GmbH or one or more of its affiliated companies

Category /Code	Description	Requirements	Exclude d from
C3 [1]	Infusion time for the investigational treatment outside of CTP specific boundaries	Infusion duration of xentuzumab given < 50 minutes or > 200 minutes (infusion time should be from 60 to 180 minutes, but the thresholds above are accepted). The exact duration of the infusion should be calculated taking interruptions into account. In case of missing administration times, the deviation will not be considered important if administration according to protocol = 'Yes'	None
C4 [2]	Patient assignment not followed	Patients do not receive the initial treatment they were allocated to	None
C4. 1	Randomisation not followed	This dose not apply for this trial	None
C4. 2	Treatment allocation not followed	Patients do not receive the initial treatment they were allocated to	None
D [2]	Concomitant medication		
D1	Prohibited treatment during trial conduct phase	All cohorts: At least one of exclusion criteria EX2, EX26-27 is met or Indicated by medical review of concomitant therapy use during study treatment.	None
E [2]	Missing Data		

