7.8.1 Adverse events

The analyses of AEs will be descriptive in nature. All analyses will be based on the number of patients with AEs (not the number of AEs).

For analysis multiple AE occurrence data on the CRF will be collapsed into an AE event provided that all of the following applies:

- All AE attributes are identical (Lowest Level Term (LLT), Common Terminology Criteria for Adverse Events (CTCAE) grade, action taken with trial medication, therapy required, seriousness, reason for seriousness, relationship, outcome, AE of special interest)
- The occurrences were time-overlapping or time-adjacent (time-adjacency of 2 occurrences is given if the second occurrence started on the same day or on the day after the end of the first occurrence)

For further details on summarisation of AE data, please refer to [\(5\)](#) and [\(6\)](#).

Adverse events will be coded with the most recent version of MedDRA. The severity of AEs will be scaled according to CTCAE (CTCAE version 4.03 [\(11\)](#)).

The analyses of adverse events will be based on the concept of treatment-emergent adverse events. That means that all adverse events with an onset between first treatment administration until end of the REP will be assigned as 'on treatment'. All adverse events occurring before first drug intake will be assigned to 'screening' and all adverse events occurring after the residual effect period will be assigned to 'post-treatment'; these AEs will be displayed in listings only. First drug intake includes the run-in period for Cohort E and F. Adverse events will be displayed by the initial dose of study medication administered on the first day of treatment .

An overall summary of adverse events will be presented. The frequency of patients with adverse events will be summarised by treatment, primary system organ class and preferred term. Similar summaries will be produced for the BIcMQ SARS-COV-2-infections.

Proprietary confidential information © 2021 Boehringer Ingelheim International GmbH or one or more of its affiliated companies

Separate tables will be provided for patients with drug-related adverse events, adverse events leading to dose reduction, adverse events leading to discontinuation, serious adverse events, serious drug-related serious adverse events, adverse events leading to death, other significant adverse events, adverse events of special interest, and adverse events fulfilling the DLT definition.

Sorting order:

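### SAP 6.1 labels the MTD evaluation by the dose assigned, SAP 7.8.1 labels adverse events by the dose administered, and no rule covers a patient for whom the two differ

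*SAP*

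**What the plan says.** SAP 6.1 covers both the on-treatment period and the MTD evaluation period with one rule: "the initial trial medication assigned at the beginning of the first treatment cycle will be used as label of the analysing treatment". SAP 7.8.1 uses a different word for the safety tables, which include a separate table of events meeting the DLT definition: "Adverse events will be displayed by the initial dose of study medication administered on the first day of treatment".

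SAP 7.4.1 takes the MTD from the Bayesian logistic regression model (BLRM) in protocol section 7. Protocol 7.1 defines each single-agent parameter to "be the probability of having a DLT when giving dose" of that drug. One of its two criteria for having reached the MTD counts patients treated at that dose.

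Table 6.2: 1 in the SAP foresees a mismatch. Deviation C4.2 reads "Patients do not receive the initial treatment they were allocated to", and its exclusion column says none. SAP 6.1 does contain an exception, "Handling of patients where cohort assignment has not been followed will be handled on a case-by-case basis", but it concerns the cohort. The dose label is set in a separate paragraph with no exception.

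**The concern.** The two labels agree for every patient who starts on the allocated combination. They part only for a C4.2 patient, and there the plan gives one answer for the MTD table (assigned) and another for the adverse event tables (administered), without saying which enters the model.

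A dose-toxicity model needs the dose received. Nothing in this trial is randomised (protocol 7.6), so analysis as assigned protects no comparison. The primary endpoint of cohorts A to D could then carry a DLT, or a DLT-free course, at a combination the patient did not take, and the DLT counts in two parts of the report could disagree.

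The MTD set does not clearly remove such a patient. SAP 6.3 drops replaced patients and expansion-cohort patients, and the replacement reasons in protocol 3.3.5 do not name a wrong starting dose.

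**Working it through.** **Inputs.** Cohort A prior from protocol Table 7.1: 3 (two-component mixtures weighted 0.9 and 0.1 for each drug; interaction η normal with mean 0 and SD 0.707). Reference doses are 1000 mg and 150 mg. The overdose range is a DLT rate of 0.33 or more, with a limit of 25% (protocol 7.1). Combinations below are written xentuzumab/abemaciclib; protocol Table 10.6: 1 prints them in the reverse order.

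**Model (protocol 7.1).**
- Each drug k: logit(π_k) = log(α_k) + β_k·log(d_k/d_k*).
- No interaction: π⁰ = π₁ + π₂ − π₁π₂.
- With interaction: odds(π) = odds(π⁰)·exp(η·(d₁/d₁*)·(d₂/d₂*)).
- DLT counts are binomial at each combination.

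Posteriors come from several million draws from the prior, weighted by the binomial likelihood. Simulation error is about 0.001 or less.

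**Reproducing the protocol.** Overdose probability at 1000/150:

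| Data at 1000/150 | Recomputed | Printed |
|---|---|---|
| Prior only | 0.098 | 0.098 |
| 0 DLTs in 3 | 0.026 | 0.027 |
| 1 in 3 | 0.144 | 0.141 |
| 2 in 3 | 0.425 | 0.430 |

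All agree within 0.005, so the model is implemented as written.

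**Effect of the label.** Suppose one patient assigned 1000/150 had a DLT-free first course but actually started at 1000/100. As assigned, all patients sit at 1000/150. As received, that patient moves to 1000/100.

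| DLTs / patients assigned 1000/150 | As assigned | As received | Crosses 25%? |
|---|---|---|---|
| 4 / 12 | 0.238 | 0.263 | yes |
| 2 / 5 | 0.244 | 0.277 | yes |
| 2 / 6 | 0.183 | 0.209 | no |
| 2 / 3 | 0.424 | 0.482 | no, above in both |
| 3 / 6 | 0.425 | 0.469 | no, above in both |

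**Other moves with 4 in 12.** A patient with a DLT moved to 1000/100 gives 0.243. A DLT-free patient moved to 750/150 gives 0.249, and a patient with a DLT moved there gives 0.230. None crosses.

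**Wider scan.** With 3, 6, 9 or 12 patients at 1000/150 and DLT counts up to half of them, moving one patient to 1000/100 or 750/150, with or without a DLT, changes the 25% decision only in the 4-in-12 case in the table. The 2-in-5 case also crosses, but five is not a multiple of the three-patient groups simulated in protocol Appendix 10.6.

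**The case against.** The best case for leaving the text alone has four parts.

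**The word may be harmless.** Both sentences say initial, and the 6.1 wording may only be meant to separate the starting dose from later individual reductions. SAP 7.4.1 also defers to the protocol model, which already uses the dose given. This is a fair reading of intent, but 6.1 names the MTD evaluation period explicitly and says the opposite. A label by the combination started keeps the distinction from later reductions.

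**The patient might be removed anyway.** The MTD set requires full evaluability, protocol 3.3.5 allows replacement of patients not evaluable for DLT, and SAP 7.4.1 decides replacement case by case. That makes the wrong count possible, not certain. This part stands.

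**Misdosing is unlikely and the dosing decisions are past.** Protocol 4.1.3 has the dose confirmed before inclusion, and 4.1.4 assigns xentuzumab and abemaciclib through the interactive response system. SAP version 2.0 is dated 25 October 2021, and SAP section 3 says the safety analyses after cohorts A to D had been performed. This stands too: the label now affects reporting and any later model run, not the dose decisions already taken.

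**The crossing was found at the threshold.** True. Most data patterns do not cross.

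A reader might also infer that cohorts D1 and D2 need the same repair, because SAP 6.1 says "Patients will be analysed according to the cohort initially assigned" and an unmet visceral-status criterion ("Cohort B, C, D, F, D1 and D2: Inclusion criteria IN9-12 is not met") excludes nobody. The documents do not support that step:
- The two cohorts are analysed separately and descriptively, with no planned test between them (protocol 7.2, 7.3 and 7.3.1).
- If two of 30 patients were swapped each way at the planning rates, D1 would move to (28×60 + 2×69)/30 = 60.6% and D2 to (28×69 + 2×60)/30 = 68.4%, a shift of 0.6 points each.
- The sites listed in protocol 5.6, "number and locations of metastatic sites (bone, liver, lung, peritoneum, brain, other) at the study entry", do not separate pleural disease or effusions, which the visceral definition in protocol 3.1 requires. A derivation from those categories could misclassify correctly enrolled D1 patients.
- Analysis by enrolled cohort with deviations tabulated is a defensible choice.

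**Conclusion.** The inconsistency is real and narrow. SAP 6.1 conflicts with SAP 7.8.1 and with the protocol model over which starting dose labels a patient, and the SAP's own deviation list foresees the patient for whom it matters.

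The size is small: one misallocated patient shifts the overdose probability at 1000/150 by about 0.03 where the data lie near the limit (0.263 − 0.238 = 0.025; 0.277 − 0.244 = 0.033). It changes the 25% decision only there. This rests on hypothetical DLT counts, one assumed misallocation to another planned level, and the cohort A prior. The documents report no such case, so it would go too far to say that the MTD was estimated at wrong doses. Severity: minor.

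**What to change.** In SAP 6.1, replace the assigned medication as the label with the dose combination actually started: on Course 1 Day 1, or at the first dose of the run-in for cohort E. Apply it to the MTD evaluation and all safety outputs, so that 6.1 matches 7.8.1. Add one sentence: a patient with deviation C4.2 who stays in the MTD set enters the BLRM at the combination received. Leave the D1 and D2 cohort rule as it is.

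The cost is about two sentences of SAP text. No new data are needed, since administration is already recorded, and outputs change only if a C4.2 patient exists.

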6.2 IMPORTANT PROTOCOL DEVIATIONS

No per protocol set (PPS) analysis will be performed for this study, hence, no patient will be excluded from the analyses (except those with missing informed consent or not adhering to age limit). However patients with potentially important protocol deviations (IPDs) will be documented. The following list of potentially IPDs in [Table 6.2: 1](#) will be used; note that this is a working list and may not be finalised until the final Blinded Report Planning Meeting (BRPM) or DBL meeting (but prior to database lock for the primary analysis). Potentially important protocol deviations will be handled according to BI standards ([8](#)).

During the study conduct, protocol deviation should be monitored and guidance for improving / teaching the respective sites should be discussed during the study Medical Quality Review Meetings (MQRMs).

A frequency table of the IPDs will be produced. In addition, a frequency table of all COVID-19 related non-important and important PDs will be produced.

Proprietary confidential information © 2021 Boehringer Ingelheim International GmbH or one or more of its affiliated companies

Table 6.2: 1 Important PDs

Category /Code		Description	Requirements	Exclude d from
A [1]		Entrance criteria not met		
	A1	Diagnosis of trial disease questionable	Cohort A and E: Inclusion criteria IN6 is not met. or Cohort B, C, D, F, D1 and D2: Inclusion criteria IN6-8 is not met.	None

Proprietary confidential information © 2021 Boehringer Ingelheim International GmbH or one or more of its affiliated companies

Category /Code	Description	Requirements	Exclude d from
A2	Prohibited baseline condition, diagnosis or treatment	
All Cohorts: Inclusion criteria IN3-5 is not met or Cohort A: Inclusion criteria IN7-8 is not met or Cohort B, C, D, F, D1 and D2: Inclusion criteria IN9-12 is not met or Cohort E: Inclusion criteria IN7-9 not met or Cohort F: Inclusion criteria IN13-14 not met or All cohorts: At least one of exclusion criteria EX1, EX3, EX5-6, EX10, EX12-13, EX15-19, EX21, EX25 is met. or Prohibited medication use (or surgery) before the treatment period of the trial, that is, All cohorts: At least one of exclusion criteria EX4, EX7-9, EX11, EX20, EX22-24 is met
	None
A3	Laboratory result indicating inadequate organ function at screening	
All cohorts: Exclusion criteria EX14 is met or Both screening and baseline (defined in Section 6.7 of this document) laboratory results are missing.
	None

Proprietary confidential information © 2021 Boehringer Ingelheim International GmbH or one or more of its affiliated companies

Category /Code		Description	Requirements	Exclude d from
B [1]		Legal Criteria		
	B1	Informed consent not available / not done	Written informed consent is not available/done	All
	B2	Informed consent too late	Inclusion criterion IN2 is not met.	None
	B3	Age limit for patient inclusion not adhered to	Inclusion criterion IN1 is not met.	All
C [2]		Trial medication and randomisation		
	C1 [2]	Time window deviation for procedures performed at screening	Assessment at screening not within 28 days prior to first treatment. Create listing, decision at MQRM / RPM.	None
	C2 [2]	Trial medication not given according to protocol	Dose reduction scheme not followed (see CTP Section 4.1.4.2); Administration of trial medication(s) not compliant Indicated by medical review (i.e. where Administration of xentuzumab according to the protocol = 'No' and associated comments, or compliance data from letrozole, anastrozole, fulvestrant or abemaciclib with associated comments) Please note: This excludes the investigational treatment given outside the boundaries specified in the CTP (covered in Category C3).	None

Proprietary confidential information © 2021 Boehringer Ingelheim International GmbH or one or more of its affiliated companies

Category /Code	Description	Requirements	Exclude d from
C3 [1]	Infusion time for the investigational treatment outside of CTP specific boundaries	Infusion duration of xentuzumab given < 50 minutes or > 200 minutes (infusion time should be from 60 to 180 minutes, but the thresholds above are accepted). The exact duration of the infusion should be calculated taking interruptions into account. In case of missing administration times, the deviation will not be considered important if administration according to protocol = 'Yes'	None
C4 [2]	Patient assignment not followed	Patients do not receive the initial treatment they were allocated to	None
C4. 1	Randomisation not followed	This dose not apply for this trial	None
C4. 2	Treatment allocation not followed	Patients do not receive the initial treatment they were allocated to	None
D [2]	Concomitant medication		
D1	Prohibited treatment during trial conduct phase	All cohorts: At least one of exclusion criteria EX2, EX26-27 is met or Indicated by medical review of concomitant therapy use during study treatment.	None
E [2]	Missing Data		
E1	Imaging assessments not done according to CTP instructions	Imaging assessment should be performed at screening and several time points thereafter (see TSAP Section 6.7.2).	None
E2	Pregnancy test not done according to CTP instructions	Only for Studies where pregnancy tests are required	None

Proprietary confidential information © 2021 Boehringer Ingelheim International GmbH or one or more of its affiliated companies

Category /Code	Description	Requirements	Exclude d from
F [2]	Trial Specific protocol deviations		
	F1 Other protocol deviations affecting patient rights or safety	Manual PDs will be collectively captured.	None
Q [2]	Non-important COVID-19 related		
	Q1 Missed examination	With inactivated forms or records, but without inactivated visit date	None
	Q2 Missed visit	With inactivated visit date	None

[1] IPD will be derived automatically

[2] IPD will be identified via individual review at MQRM/RPM/DBLM.

